for the second consecutive blood glucose value >150 mg/dL but ≤ 300 mg/dL and continue per protocol for a maximum duration of 48 hours. Exenatide will be administered by intravenous infusion (50 ng/min for 30 minutes, then start exenatide infusion 25 ng/min) for the second consecutive blood glucose value >150 mg/dL but ≤ 300 mg/dL and continue per protocol for a maximum duration of 48 hours (dose, route, titration schedule, and duration). Exenatide will be prepared by the Investigational Drug Service. The exenatide infusion initiation and maintenance protocols are outlined in Tables 1&2 of the attached study protocol. The exenatide infusion blood glucose goal will be 110-180 mg/dL. During the exenatide infusion, glucose measurements will be obtained hourly. The exenatide infusion will be temporarily discontinued for blood glucose <110 mg/dL. The exenatide infusion will be restarted once the blood glucose level is at least 110 mg/dL. Episodes of hypoglycemia will be treated according to the following guidelines: 1) glucose <70 mg/dL will be provided 25 mL of dextrose 50% (1/2 amp) 2) blood glucose will be re-checked in 5 minutes; if mental status changes caused by hypoglycemia are not reversed or blood glucose remains <70 mg/dL, the above dextrose administration will be repeated, 3) serum glucose will be checked hourly after dextrose administration and the episode has resolved. Exenatide infusion will be restarted beginning with the second hourly glucose check that is ≥ 110 mg/dL. Insulin sensitive sliding scale using formulary rapid acting insulin will be used for blood glucose 181-300 mg/dL starting at the 2nd hourly glucose check (≥ 2 hours since exenatide initiation). The physician will be notified for any blood glucose >300 mg/dL for initiation of a rescue insulin infusion protocol. All glucose values will be documented in the ICU Electronic Documentation System.

Table 1: Exenatide Infusion Initiation Protocol

Glucose (mg/dL)	Action
151-300	
Give exenatide 50 ng/min for 30 minutes, then start exenatide infusion 25 ng/min
 
Give prokinetic agent per NSICU protocol (reglan, erythromycin, etc)
 
Check glucose hourly
 
Monitor blood pressure continuously during exenatide infusion. If SBP <100 mmHg, contact physician. Decision to discontinue exenatide infusion will be made at the discretion of the treating physician.

Table 2: Exenatide Infusion Maintenance Protocol

Glucose (mg/dL)	Action

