3. Glycemic Variability Protocol: The Guardian REAL-Time Continuous Glucose Monitoring System (CGMS, Medtronic MiniMed, Northridge, CA) will be used to assess glycemic variability. The CGMS device carries an FDA-approved indication to supplement but not replace routine standard monitoring in patients. As such, the nursing staff will be blinded to the CGMS readings. All therapeutic decisions will be based upon standard of care glucose monitoring as outlined in the glycemic control protocol.

The CGMS is composed of a subcutaneous sensor that uses the glucose oxidase reaction for generation of an electrical current. A wireless transmitter connects to the sensor, and the signal is analyzed and converted to a measurement of the subcutaneous glucose level by a pager-sized device. Glucose levels are measured and recorded every 5 minutes. The subcutaneous glucose sensor will be deployed using the insertion kit available by the manufacturer. The sensors will be preferentially placed in the anterior abdomen. In the event the anterior abdomen is not available, the sensor will be placed in the upper thigh. Routine blood glucose measurements will be obtained hourly while the patient is receiving exenatide for purposes of calibration of the CGMS. After the initial calibration, the CGMS will be calibrated every 12 hours at a minimum. Sensors will be monitored daily by an investigator and 1 day after removal. The CGMS will be performed for 72 hours (48 hours during study drug infusion and an additional 24 hours during follow-up after study drug is discontinued).

4. Pharmacokinetic Protocol:

All patients admitted to the NSICU that meet the eligibility criteria will be approached for consent of blood samples obtained for pharmacokinetic analysis. Blood samples will be collected at 0, 12, 24, 36, and 48 hours after the start of the infusion. Approximately 30 mL of blood will be collected over 48 hours for pharmacokinetic sampling. The exenatide concentrations will be processed by Tandem Labs. An 8-hour urine collection for measuring creatinine clearance will be performed as the primary method of measuring renal

function. Eight-hour urine collections will be obtained on a daily basis for 72 hours (48 hours during study drug infusion and an additional 24 hours during follow-up after study drug is discontinued).

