2 DATA MONITORING COMMITTEE AND OTHER EXTERNAL COMMITTEES

Not applicable

8. Measurements: Blood glucose from the arterial line will be measured at baseline (prior to exenatide), hourly during the 48 hour exenatide infusion per protocol (table 2) and continue for an additional 24 hours following exenatide discontinuation. The continuous glucose monitor will measure the interstitial glucose level every 5 minutes beginning at baseline (prior to exenatide) until 24 hours following exenatide discontinuation. Blood samples for pharmacokinetic analysis will be collected in serum separator tubes at 0, 12, 24, 36 and 48 hours after the start of the infusion. Eight-hour urine collections will be obtained on a daily basis for 72 hours (48 hours during study drug infusion and an additional 24 hours during follow-up after study drug is discontinued). Microdialystate concentrations will be collected at baseline (prior to exenatide), and hourly during the 48-hour exenatide infusion for parameters of energy metabolism (glucose, pyruvate, lactate, lactate:pyruvate ratio), glutamate (marker of cerebral ischemia), and glycerol (marker of cell membrane degradation) and for an additional 24 hours following study drug discontinuation. Blood pressure will be measured continuously throughout the study period. Intracranial pressure (ICP) will be measured continuously during the exenatide infusion. Intracranial pressure values will be recorded at baseline (prior to exenatide) and daily mean ICP and cerebral perfusion pressure values will be reported. Baseline demographic information (e.g. gender, age, ethnicity) and disease severity information [e.g. Glasgow coma score, SOFA score (Sequential Organ Failure Assessment), Hunt Hess classification, Fisher grade, primary diagnosis, past medical history (including measurement of hemoglobin A1c), neurologic exam/computed tomography scan abnormalities] will be collected. The ICU day of study drug administration will be recorded and the total hospital and ICU lengths of stay will be recorded.

9. Data Management: Each participant will be assigned a unique identification number. No personal identification will be used. All study files will be stored in locked cabinets in the Principal Investigator's office in the Pharmacy Administration Department. Data will be entered into the study database using double entry (entry and verification) and will be checked for missing or ineligible responses.

10. Outcomes

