10.1 The following feasibility endpoints are based upon prior literature (Nice-Sugar and Exenatide Study in the Cardiac ICU):

Proportion of patients experiencing severe hypoglycemia (<40 mg/dL), Proportion of patients achieving plasma glucose goal (110-180 mg/dL), Proportion of patients experiencing nausea requiring discontinuation of exenatide therapy

10.2 The following descriptive endpoints are included for describing experience with exenatide use in the NSICU population:

Average blood glucose value during exenatide infusion (48 hours), percent time in glucose range (48 hours), mean time to reach plasma glucose goal (110-180 mg/dL), variability outcome (SD)-MADGE, mean insulin use required (units/kg body weight), proportion of subjects requiring rescue insulin infusion protocol, number of hypoglycemic episodes (<80 mg/dL)/total number of glucose measurements (48 hours), number of subjects with >1 hypoglycemic episode (<80 mg/dL)/total number of subjects (48 hours), correlation of exenatide concentrations with creatinine clearance during infusion, elimination rate constant and area under the concentration-time curve utilizing concentrations after discontinuation of infusion, side effects and adverse events (AEs and SAEs), average daily ICP and CPP during study drug infusion, number of hypotensive episodes (SBP<100 mmHg) (48 hours), number of subjects with >1 hypotensive episode/total number of subjects (48 hours). Other adverse effects will be collected specifically assessing any alterations in gastric motility.

In patients receiving invasive intracranial multimodal monitoring as part of their standard of care, the following endpoints associated with exenatide use will be described:

Percent time outside of range for energy metabolism (glucose <0.7 mmol/L and lactate:pyruvate ratio > 40), glutamate (marker of cerebral ischemia), and glycerol (marker of cell membrane degradation) parameters (48 hours).

Based upon prior literature, the prespecified criteria for determining feasibility include the following: 1) no more than 6 patients (25%) experiencing severe hypoglycemia (<40 mg/dL); 2) at least 18 patients (75%) achieving the plasma glucose goal (110-180 mg/dL); 3) no more than 6 patients (25%) experiencing nausea leading to exenatide discontinuation. These criteria will be utilized to determine whether a future efficacy trial will be pursued.

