11. Sample size and justification: A sample size was determined using prior exenatide in critically ill patients studies and patient screening information at our site. Based upon this data, we determined to enroll 24 patients who complete 48 hours of exenatide infusion and continuous glucose monitoring. In eligible patients, cerebral microdialysis monitoring will also be performed. It is estimated based on proposed eligibility criteria that 24% (n = 200) patients admitted to the NSICU will be eligible for enrollment annually. With an approximate rate of enrollment at 15 – 20%, we are confident we could enroll 30 – 40 subjects annually.

12. Data analysis plan: Prior to analysis, data will be examined for errors, outliers, and asymmetry. When appropriate, transformations will be used to reduce asymmetry. An intent-to-treat analysis (defined as all individuals consented in the study) will be utilized. Descriptive statistics will be performed. Data will be expressed as means \pm standard error (SE) or success rates and corresponding 95%CI for continuous and

dichotomous outcomes, respectively. Analyses will be completed using the statistical software package SAS, version 9.2 (SAS institute, Cary, North Carolina).

13. Ethical consideration: The consent procedures will be reviewed and approved by the Institutional Review Board. All subjects will provide written informed consent via proxy. The informed consent process will allow the proxy to gain an in-depth knowledge of the study purposes and procedures and allow them to make informed decisions about willingness to proceed. Participation is voluntary. The proxy will be encouraged to ask questions and will be assessed for adequate understanding.

Exenatide required: yes

Placebo required: no

Clinical study duration of treatment: Subjects will be exposed to exenatide treatment for 48 hours.

Clinical study dosing schedule and frequency: exenatide 50 ng/min for 30 minutes, start exenatide infusion 25 ng/min x 48 hours

Clinical study number of sites: one

Clinical study expected number of subjects screened: It is estimated based on proposed eligibility criteria that 24% (n = 200) patients admitted to the NSICU will be eligible for enrollment annually with an approximate rate of enrollment at 15-20%.

Clinical study expected number of subjects enrolled: 24

Clinical study expected number of subjects to complete study: 24

Planned Study Start Date: January 1, 2015

Planned Study End Date: June 30, 2016

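### The elimination rate constant and AUC are defined on post-infusion concentrations, but no scheduled PK sample follows the infusion in a patient who completes it

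*Combined protocol and SAP*

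**What the plan says.** Section 10.2 includes among the descriptive endpoints the "elimination rate constant and area under the concentration-time curve utilizing concentrations after discontinuation of infusion".

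The sampling times are given twice and agree. Methodology item 4 (Pharmacokinetic Protocol) says: "Blood samples will be collected at 0, 12, 24, 36, and 48 hours after the start of the infusion". It adds: "Approximately 30 mL of blood will be collected over 48 hours for pharmacokinetic sampling". Item 8 (Measurements) says that the PK blood "will be collected in serum separator tubes at 0, 12, 24, 36 and 48 hours after the start of the infusion".

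On the length of infusion, item 2 (Glycemic Control Protocol) has it "continue per protocol for a maximum duration of 48 hours". The dosing line after item 13 reads "exenatide 50 ng/min for 30 minutes, start exenatide infusion 25 ng/min x 48 hours", which taken literally is 48.5 hours. Item 2 also allows pauses: "The exenatide infusion will be temporarily discontinued for blood glucose <110 mg/dL".

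Other measurements do run on. Item 8 continues arterial glucose, continuous glucose monitoring and microdialysis for 24 hours after the drug stops, and for urine it says "Eight-hour urine collections will be obtained on a daily basis for 72 hours". PK blood is not among these.

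Items 1 and 11 aim for 24 patients who complete.

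**The concern.** An elimination rate constant is the slope of log concentration against time once drug input has ceased, so it needs at least two concentrations on the declining curve. The plan says that this is where the data will come from, yet it schedules no draw there.

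Aim 2 exists because augmented renal clearance may remove exenatide faster than expected. The rate constant is the listed endpoint that measures elimination directly. If the plan is followed exactly, that endpoint has no planned source data in any completer, and a missing sample cannot be recovered at analysis. Any values that did appear would come from patients whose infusion happened to stop or pause early. That is a selected group, and the endpoint is not defined for it.

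**Working it through.** The plan gives no calculated figure to reproduce. The check compares the scheduled times with the end of infusion.

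**Inputs.** Draws at 0, 12, 24, 36 and 48 h from the start (items 4 and 8). Infusion end at 48 h (item 2) or 0.5 + 48 = 48.5 h (dosing line after item 13). 24 completers (items 1 and 11). About 30 mL for five draws (item 4).

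**Draws after the stop, per patient**

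| Infusion ends | Draws strictly after | Draw exactly at the end |
|---|---|---|
| 48 h | 0 of 5 | 1 (48 h) |
| 48.5 h | 0 of 5 | 0 |
| Early, 36 h to <48 h | 1 | not applicable |
| Early, 24 h to <36 h | 2 | not applicable |
| Early, 12 h to <24 h | 3 | not applicable |
| Early, before 12 h | up to 4 | not applicable |

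**Across the study.** 24 × 5 = 120 scheduled draws. Of these, 24 × 1 = 24 are pre-dose, 24 × 4 = 96 are during or at the end of infusion, and 24 × 0 = 0 come after it. Even a 48 h draw taken just after the stop is a single point, and a slope needs two.

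**Could the on-infusion samples give the rate constant instead?** At steady state, clearance = infusion rate / concentration. The rate constant is clearance / volume of distribution, and steady-state samples do not supply the volume. Only the rise towards steady state carries information on the rate constant, and the first draw after time 0 is at 12 h. The documents give no half-life, so I assume 1, 2 and 4 h, with a one-compartment model and the stated rates (50 ng/min for 0.5 h, then 25 ng/min). With k = ln 2 / half-life, for t ≥ 0.5 h:

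C(t)/Css = (1 − e^(−kt)) + (1 − e^(−0.5k)) · e^(−k(t − 0.5))

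| Assumed half-life | C(12 h)/Css | Time to 90% of steady state from zero (log2(10) = 3.32 half-lives) | Fraction left 12 h after a stop |
|---|---|---|---|
| 1 h | 1.00 | 3.3 h | 0.02% |
| 2 h | 0.99 | 6.6 h | 1.6% |
| 4 h | 0.89 | 13.3 h | 12.5% |

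By 12 h the rise is complete or nearly so, and little information on the rate constant remains. The last column shows why chance samples from early stoppers, 12 h apart, are a poor substitute.

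**What the schedule does support.** AUC(0-48) can be computed, but on a 12 h grid the linear trapezoid cuts off the early rise. In units of Css × h, under the same model:

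| Assumed half-life | Trapezoid | True | Difference |
|---|---|---|---|
| 1 h | 42.00 | 47.06 | −10.8% |
| 2 h | 41.85 | 45.61 | −8.3% |
| 4 h | 40.44 | 42.73 | −5.4% |

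**Blood volume.** 30 / 5 = 6 mL per draw, if the five volumes are equal.

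**The case against.** The mismatch itself is hard to dispute: two sections give the same five times, and no section schedules a later draw. The best counter-case concerns weight and detail.

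- **Weight.** The endpoints are descriptive, and none of the three feasibility criteria uses a PK quantity. The stated method for Aim 2, concentrations set against measured creatinine clearance, remains achievable. This stands, and it limits the severity.
- **Some samples may exist.** Early stoppers, or a pause that spans a draw, could yield an off-infusion concentration. True, but only by chance, and not in a planned completer without pauses. It is fair to insist that the claim concerns scheduled samples.
- **The counts are idealised.** The 96 assumes no pauses. The 120 is an upper bound if a proxy can decline PK sampling. This stands, but the zero after the stop does not depend on it.
- **The cost to the correlation may be smaller than it looks.** Aim 2 wants concentration and urinary clearance measured concurrently. One 8-hour urine collection a day gives about two during infusion, and each window holds at most one draw on a 12 h grid. That is about 2 × 24 = 48 truly concurrent pairs, not 96. Moving a draw that lies outside a urine window would cost no concurrent pair. This stands as a refinement of the cost.
- **The 48 h draw is not the end of infusion on the 48.5 h reading.** It falls 30 minutes before the stop. In the model above the level has reached steady state by then, so it still serves as the end-of-infusion concentration, provided the infusion was not recently paused.

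**Conclusion.** The concern holds. Sections 10.2, 4 and 8 cannot all be carried out as written in a patient who completes the infusion. None of the five scheduled draws per completer, and none of the 120 across 24 completers, falls after the infusion stops, whichever reading of its length is used. The rate constant and AUC, as worded, have no planned data.

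This rests only on times stated in the protocol. The half-lives of 1 to 4 h are assumptions. They affect only the side results on steady state and trapezoid error, not the conclusion.

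The point should be fixed but does not threaten the study's main purpose. The incidence of augmented renal clearance, the correlation of concentration with creatinine clearance, AUC(0-48) and a near-steady-state clearance all remain obtainable. Pauses may also disturb that correlation, by an amount that the documents do not allow one to estimate.

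**What to change.** Reconcile items 4, 8 and 10.2 in one of two ways.

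**(a) Change the endpoints to fit the samples.** Replace them with AUC(0-48) and on-infusion clearance (infusion rate / concentration), and relate that clearance to measured creatinine clearance. Use only samples near steady state, for example at least 3.3 half-lives after the start or last restart, and state the half-life used. Record pause and restart times, and flag or exclude samples taken during or soon after a pause. State the AUC method, because a plain linear trapezoid would be about 5% to 11% low under the assumed half-lives. The cost is an endpoint amendment and a small addition to data capture, since no section explicitly asks for pause and restart times. No extra blood is needed. The rate constant is given up.

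**(b) Change the samples to fit the endpoints.** Keep the endpoints and place one or two draws at specified times counted from the actual stop, with the 48 h draw as the end-of-infusion point. Record actual stop and draw times. One later draw is the arithmetic minimum; two or more would allow a check of the fit. The spacing needs a half-life, which the plan should state. The costs are:

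- Moving one on-infusion draw leaves 96 − 24 = 72 on-infusion samples; moving two leaves 48.
- Moving the 0 h draw keeps all 96 but loses the baseline.
- Adding a draw keeps everything, at about 6 mL per patient.

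The 48-hour collection window in item 4 and the schedule in item 8 would need amending. The two statements of infusion length should also be reconciled, so that the stop time from which these draws are counted is unambiguous.

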A potential role for incretin-based therapy in the management of critically ill patients with hyperglycemia exists. Glucagon-like peptide-1 (GLP-1) is the most well characterized naturally occurring incretin hormone. On ingestion of meals, GLP-1 is secreted from L-cells of the small intestine and subsequently enhances glucose-dependent insulin secretion, suppresses postprandial glucagon secretion from pancreatic alpha-cells, slows gastric emptying, and signals satiety.⁴³⁻⁴⁶ Because the former effects are glucose dependent, the use of GLP-1 does not appear to be associated with hypoglycemic risk. The major limitation of endogenous GLP-1 is its relatively short half-life due to degradation by the enzyme dipeptidyl peptidase IV (DPP-IV).⁴⁷ Exenatide, a DPP-IV resistant GLP-1 receptor agonist, has recently been added to the therapeutic armamentarium targeting hyperglycemia. The effect of GLP-1-based therapy on hyperglycemia following neurologic injury has recently been evaluated in patients with acute ischemic stroke.⁴⁸ Daly and colleagues administered exenatide subcutaneously in eleven patients over a median duration of six-days. They reported no symptomatic hypoglycemia or serious adverse effects and a low rate of hyperglycemia (4.9%; defined as > 155 mg/dL); however, glycemic variability was not assessed in this study. Additionally, the incidence of nausea and vomiting with subcutaneous administration was high with 55% and 45% of patients experiencing these adverse effects, respectively. Despite these promising results with subcutaneous administration, other studies have evaluated exenatide's therapeutic use as a continuous infusion in critically ill populations and have reported low incidence of gastrointestinal side effects.⁴⁹⁻⁵² Therefore, *there is a need* to evaluate the feasibility of exenatide infusion in critically ill patients with acute brain injury and investigate its impact on glycemic variability.

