6. General Management Protocol: All patients will be managed using standard NSICU protocols. ICP will be kept < 25 mmHg using a stepwise management strategy (management strategies will be recorded). Patients fluid will be maintained with crystalloids without glucose and enteral nutrition will be started as soon as possible. No patients will receive intravenous or oral steroids for their brain injury. Seizure prophylaxis will be provided per protocol for 7 days and sedation/analgesia will be provided as needed and titrated to standard monitoring scales or ICP. A prokinetic agent will be initiated for study subjects per NSICU protocol. Blood pressure will be monitored continuously throughout the study period for all subjects. All medications received during study drug infusion will be recorded.

7. Safety Data:

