1 ADVERSE EVENTS

An ***Adverse Event (AE)*** is defined as any new untoward medical occurrence or worsening of a pre-existing medical condition in a patient or clinical investigation subject administered an investigational (medicinal) product and that does not necessarily have a causal relationship with this treatment. An AE can therefore be any

unfavorable and unintended sign (including an abnormal laboratory finding, for example), symptom, or disease temporally associated with the use of investigational product, whether or not considered related to the investigational product.

Adverse events can be spontaneously reported or elicited during open-ended questioning, examination, or evaluation of a subject. (In order to prevent reporting bias, subjects should not be questioned regarding the specific occurrence of one or more AEs.)

1.1 **Serious Adverse Events**

A ***serious AE (SAE)*** is any untoward medical occurrence that at any dose:

- results in death
- is life-threatening (defined as an event in which the subject was at risk of death at the time of the event; it does not refer to an event which hypothetically might have caused death if it were more severe)
- requires inpatient hospitalization or causes prolongation of existing hospitalization (see **NOTE** below)
- results in persistent or significant disability/incapacity
- is a congenital anomaly/birth defect
- is an important medical event (defined as a medical event(s) that may not be immediately life-threatening or result in death or hospitalization but, based upon appropriate medical and scientific judgment, may jeopardize the subject or may require intervention [eg, medical, surgical] to prevent one of the other serious outcomes listed in the definition above.) Examples of such events include, but are not limited to, intensive treatment in an emergency room or at home for allergic bronchospasm; blood dyscrasias or convulsions that do not result in hospitalization.)

Suspected transmission of an infectious agent (eg, any organism, virus or infectious particle, pathogenic or non-pathogenic) via the study drug is an SAE.

Although pregnancy, overdose, and cancer are not always serious by regulatory definition, these events must be handled as SAEs. (See Section 6.1.1 for reporting pregnancies.)

NOTE:

The following hospitalizations are not considered SAEs in clinical studies:

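### Go/no-go criterion 3 counts only stops for reported nausea, in proxy-enrolled brain-injured patients, so it can pass despite poor gastrointestinal tolerability

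*Combined protocol and SAP*

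**What the plan says.** Section 10.1 defines the endpoint as "Proportion of patients experiencing nausea requiring discontinuation of exenatide therapy". The prespecified criteria at the end of section 10.2 turn it into a limit, "3) no more than 6 patients (25%) experiencing nausea leading to exenatide discontinuation", next to one criterion on severe hypoglycemia and one on reaching the glucose goal. Of the three, the plan states: "These criteria will be utilized to determine whether a future efficacy trial will be pursued". Criterion 3 is the only one that touches gastrointestinal tolerability.

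Four other places bear on how nausea would be found and counted:

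- **Who is enrolled.** Inclusion criterion 4 requires consent through a proxy, and section 13 repeats it: "All subjects will provide written informed consent via proxy". Section 6 (General Management Protocol) allows sedation and analgesia when needed.
- **How adverse events are elicited.** Safety Data, section 1 (Adverse Events), says that "subjects should not be questioned regarding the specific occurrence of one or more AEs". The same paragraph accepts spontaneous reports, open-ended questions, examination and evaluation.
- **What else is recorded.** Section 10.2 lists adverse events, hypotensive episodes and changes in gastric motility, all as descriptive endpoints.
- **What was seen before.** Specific Aims, on a study of eleven stroke patients: "the incidence of nausea and vomiting with subcutaneous administration was high with 55% and 45% of patients". It then says that infusion studies in the critically ill found a low incidence of gastrointestinal effects, without a figure.

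**The concern.** Criterion 3 needs two things to happen: the patient makes nausea known, and exenatide is stopped because of it. The plan gives no nausea scale, no substitute for patients who cannot communicate, and no denominator of assessable patients. Tables 1 and 2 contain no step tied to nausea, so the stopping half is undefined too.

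A patient who cannot report is scored the same as a patient who had no nausea. Missed nausea can therefore only lower the count and move the result towards a go. Vomiting and altered gastric motility are signs that staff can observe without the patient's help, but on the wording a stop for either counts against no criterion. At stake is whether Aim 1, feasibility of the infusion, is tested on gastrointestinal tolerability at all before an efficacy trial is planned.

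**Working it through.** **Plan's own figure.** 6/24 = 0.25, so the stated count and percentage agree. The exact (Clopper-Pearson) 95% interval for 6/24 is 9.8% to 46.7%. The plan gives no null rate, target rate, alpha or power for this criterion, so there is no operating characteristic to reproduce.

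**Model.** Let r be the true rate of stops for intolerance if it were always recognised, and f the share of patients able to report. Assume that reporting is independent of intolerance and that only reported cases are counted. The countable rate is p = r × f, and

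P(pass) = P(X ≤ 6), X ~ Binomial(24, p).

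Both r and f are assumptions; the documents give neither.

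| r | f = 100% | f = 75% | f = 50% | f = 25% |
|---|---|---|---|---|
| 40% (p) | 0.40 | 0.30 | 0.20 | 0.10 |
| P(pass) | 10% | 39% | 81% | 99% |
| 50% (p) | 0.50 | 0.375 | 0.25 | 0.125 |
| P(pass) | 1% | 15% | 61% | 98% |

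**Check against the one nausea rate in the documents.** Carry over the 55% from the subcutaneous study and suppose that every detected case is stopped. P(pass) is then 0.3%, 8%, 50% and 96% at 100%, 75%, 50% and 25% detection. This is a stress case: 55% is an incidence, not a stop rate, and comes from another route of administration. For P(pass) to reach 90%, p must be at most about 0.170, so the product of the share detected and the share stopped must be at most 0.170/0.55 = 0.31.

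**Fixed number able to report.** With 55% nausea and every reported case stopped, P(pass) is 47% if 12 of the 24 can report and 94% if 8 can. If 6 or fewer can report, the count cannot exceed 6 and the criterion passes with certainty at any true rate.

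**Denominator.** The 25% equals 6 patients only if the denominator is 24. Methodology section 1 recruits until 24 subjects complete the protocol, and section 11 speaks of 24 who complete 48 hours of infusion. Section 12 analyses everyone consented. A patient who stops for good because of nausea does not complete 48 hours of infusion, so these passages leave open whether that patient is among the 24. If 32 were treated, 25% would be 32 × 0.25 = 8 patients, not 6.

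**The case against.** The strongest reply is that the documents never show that patients cannot report. Proxy consent concerns capacity to consent, not ability to signal nausea. Sedation is only as needed, no inclusion criterion requires coma, and the stroke study recorded nausea in 55%, so some brain-injured patients do report it. Vomiting, motility changes and hypotension are all reported beside the criteria and would not be hidden. Infusion is expected to cause few gastrointestinal effects. All of this stands, and it limits how large the effect may be. It does not change the decision rule, which uses none of the descriptive endpoints.

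Four stronger readings are tempting, and the documents do not support them.

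- *The criterion passes almost regardless of tolerability.* This needs a low reporting share that no section gives. With full reporting and a 40% rate, it passes only 10% of the time.
- *Staff may not ask at all.* The adverse-event section discourages prompting for specific events but allows open-ended questions and examination.
- *The prokinetic produces a false pass.* The plan says "A prokinetic agent will be initiated for study subjects per NSICU protocol". It is part of the regimen under test. If it lowers true nausea, the regimen is better tolerated, and that is not a measurement fault.
- *Every adverse-event stop belongs under the 25% limit.* For low blood pressure, Table 1 says "Decision to discontinue exenatide infusion will be made at the discretion of the treating physician", and such a stop does fall outside all three criteria. But in an uncontrolled ICU cohort many such stops may be unrelated to the drug. With assumed rates of 10% nausea stops and 20% background stops, the total is 30% and P(pass) falls to 39%, a likely false no-go.

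**Conclusion.** The concern holds in direction and, conditionally, in size. As worded, criterion 3 can pass despite poor gastrointestinal tolerability, because missed nausea is scored as success and stops for observable gastrointestinal signs are not counted. No other section repairs this. At an assumed 40% true stop rate, going from full reporting to half of patients able to report raises the chance of a pass from 10% to 81%. The result rests on the assumed rate, the assumed reporting share, and independence of the two. If nearly all patients can report, the criterion discriminates, within the wide uncertainty of 24 patients. If infusion causes little intolerance, a pass would be correct. The plan should be changed because it gives no means of telling these situations apart.

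**What to change.** Reword criterion 3 along these lines: *no more than 25% of all patients who receive exenatide discontinue it for gastrointestinal intolerance (reported nausea, or observed vomiting or altered gastric motility as already collected in 10.2).* State the limit as a percentage of all treated patients, and reconcile it with the completer-based recruitment wording and the all-consented analysis set.

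With it:

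- Record the reason for each stop on the case report form.
- Allow a direct nausea question in patients able to answer, as a limited exception to the no-prompting rule.
- Report nausea separately among those able to report it, with that denominator shown. The Glasgow coma score already collected under section 8 can help define the group.
- List stops for other adverse events, including hypotension, with an exact 95% interval, as a descriptive line beside the criteria and outside the 25% limit.

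The cost is revised wording, a reason-for-stopping field, a record of who could report, and a definition by the investigators of which motility changes count. The criterion becomes slightly harder to meet. No treatment or stopping rule changes.
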